DRUG: BHV-3000 (PF-07899801) (rimegepant)

STUDY NUMBER(S): BHV3000-405 (C4951011)

PROTOCOL(S) A Phase 4, Open-label Study to Evaluate the Safety and
TITLE: Tolerability of Daily Dosing of Rimegepant in Episodic Migraine
Prevention

IND NUMBER: 109886

SPONSOR: Pfizer Inc.
[name]

ORIGINAL 22 November 2021
PROTOCOL DATE:

VERSION NUMBER: 6.0

VERSION DATE: 07 August 2023

This amendment incorporates all revisions to date, including amendments made at the request of country health authorities and IRBs/ECs and any protocol administrative change letter.

PROTOCOL AMENDMENT SUMMARY OF CHANGES

Amendment 5 (Protocol Version 6.0)

Overall Rationale for the Amendment: Change in sponsorship from Biohaven to Pfizer with alignment of the protocol template.

Description of change	Brief Rationale	Section # and Name
		Substantial Modification(s)
Referenced study number BHV3000-405 to C4951011 and compound name BHV-3000 to PF-07899801 to reflect identification changes by sponsor.	Reflects change in sponsorship protocol and compound identification numbers	Throughout Document Headers Title page
Updated the planned number of subjects from 230 to 285.	Increased sample size needs in order to account for up to 40% drop out rate through 24 weeks	Study Summary (Synopsis) Section 1.5 Study Rationale Section 5.1 Number of Subjects Section 9.1 Sample Size
Clarified the procedure for unused, non-expired, and partial wallets during Open-label Treatment Phase.	Added clarity on study procedures	Section 4.3.2 Open-label Treatment Phase
Removed criteria pertaining to "Signed Written Informed Consent".	Allowed for subjects that were unable to read and/or understand English or Spanish to be included. Removed need to provide all demographic information and aligned with Pfizer's standards and processes	Section 5.2 Inclusion Criteria
Removed the exclusion criterion for patients with HIV disease.	Aligned with rimegepant prescribing information where there is no exclusion for use in patients with HIV	Section 5.3 Exclusion Criteria #2
Clarified that blood pressure must be less than 150/100 mg Hg at the screening and baseline visit.	Clarified that BP must be within range prior to dosing of IP	Section 5.3 Exclusion Criteria #2b
Removed the exclusion criterion for patients with gallstones and cholecystectomy.	Aligned with rimegepant prescribing information where there is no exclusion for use in subjects with biliary disorder	Section 5.3 Exclusion Criteria #2
Removed Gilbert's Syndrome from the exclusionary criteria.	Aligned with rimegepant prescribing information where there is no exclusion for use in Gilbert's Syndrome	Section 5.3 Exclusion Criteria #2
Clarified the exclusion criterion of narcotics.	Updated for clarity.	Section 5.3 Exclusion Criteria #2j

Amended the exclusion criterion for body mass index to $>35.0 \text{ kg/m}^2$ from $>33.0 \text{ kg/m}^2$.	Aligned definition to be inclusive of all Class 1 Obesity subjects	Section 5.3 Exclusion Criteria #2n
Updated requirement for duration of contraception use after last dose of study drug.	Aligned with Pfizer standard and processes	Section 5.3 Exclusion Criteria #4a
Amended exclusion criterion for HbA1c to $> 7.5\%$.	Allowed inclusion of well controlled diabetics aligned with rimegepant prescribing information where there is no exclusion for subjects with diabetes	Section 5.3 Exclusion Criteria #5g
Amended the hepatic exclusion criteria to allow subjects with 1.5xULN of ALT, AST and 1.5xULN of Total Bilirubin.	Allowed for inclusion of subjects with mild LFT elevations consistent with the prescribing information where there is no exclusion for subjects with mild hepatic disease	Section 4.3.1 Screening Phase Section 5.3 Exclusion Criteria #5c and #5d
Removed specific exclusionary ECG criteria.	Allowed for investigator opinion on exclusionary ECG findings	Section 5.3 Exclusion Criteria #5b
Changed eGFR from <40 to $<30 \text{ mL/min}/1.73\text{m}^2$.	Allowed for subjects with moderate renal impairment to be included in the trial consistent with the prescribing information.	Section 5.3 Exclusion Criteria #5a
Added exclusion criterion for involvement in the conduct of the clinical trial by staff or family members.	Aligned with Pfizer protocol template	Section 5.3 Exclusion Criteria #7k
Allowed for re-screening of subjects due to prior failed eligibility criteria.	Allowed for re-screening of subjects who previously were screen failed for an amended exclusionary criterion	Section 4.3.1 Screening visit Section 5.3 Exclusion Criteria #7i
Removed “but did not participate in any multiple dose rimegepant study” from exclusion criteria.	Editorial, redundant sentence	Section 5.3 Exclusion Criteria #7f
Removed “any reason which, in opinion of the Investigator, would prevent the subject from participating in the study” from exclusion criteria.	Removed redundant exclusion criteria	Section 5.3 Exclusion Criteria #8
Removed tacrolimus from the strong CYP3A4 inhibitors list. Added telithromycin and troleandomycin to the list of strong CYP3A4 inhibitors, and avasimibe to the list of strong CYP3A4 inducers.	Aligned with nonclinical and clinical DDI information available on rimegepant	Section 16.2 Appendix 2 Inhibitors and Inducers of CYP3A4 and Inhibitors of P-glycoprotein (Not all-inclusive)

Changed term “non-migraine” to “non-headache”, and term “acute migraine” to “acute headache”.	Clarified to include broader definition of headache which includes non-migraine and migraine headache	Section 5.4 Prohibited and Restricted Concomitant Medications and Devices
Clarified that in case of DILI the PI should determine if the patient can safely continue in the study and expanded DILI definition to include subjects with abnormal hepatic function at study entry.	Updated definition to align with revised LFT exclusion criteria	Section 8.4 Potential Drug Induced Liver Injury (DILI)
Added Appendix for ECG findings of Potential Clinical Concern.	Aligned with Pfizer protocol template	Section 16.4 Appendix 4 ECG Findings of Potential Clinical Concern
Added the definition of Sponsor's Medically Qualified Individual.	Aligned with Pfizer protocol template	Section 10.7 Sponsor's Medically Qualified Individual
Updated benefit risk background information, regulatory status, and clinical development status. Added benefit risk assessment.	Updated benefit risk information to include up to date data	Study Summary (Synopsis) Section 1.3 Product Development Background Section 1.4 Benefit Risk Assessment
Updated contraception requirement for WOCBP, and removed contraception requirement for males and sections for “Women of Childbearing Potential” and “Pregnancy”.	Aligned with Pfizer standard and processes	Section 5.2 Inclusion Criteria #2b Section 5.6 Contraception Section 16.5 Appendix 5 – Contraceptive and Barrier Guidance Section 5.6 Women of Childbearing Potential (Removed) Section 8.4 Pregnancy (Removed)
Non-substantial Modification(s)		
Updated protocol synopsis.	Aligned with Pfizer protocol template	Study Summary (Synopsis)
Removed “Male and female” from inclusion criteria #2a.	Aligned with Pfizer protocol template	Section 5.2 Inclusion Criteria #2a
Removed the bullet name of “Other Inclusion Criteria” for previous inclusion criteria #6.	Aligned with Pfizer protocol template	Section 5.2 Inclusion Criteria #3
Added galcanezumab and eptinezumab as prohibited concomitant use of CGRP antagonists, updated the generic and trade names.	Added comprehensive list of CGRP antagonists instead of examples for clarity	Section 5.2 Inclusion Criteria #1e, ii
Clarified that this amendment incorporates all revisions to date, including amendments made at the request of country health authorities and IRBs/ECs and any PACL.	Aligned with Pfizer protocol template	Title page

Added the detail that this is a post marketing required study.	Clarified that this is a post marketing required study.	Study Summary (Synopsis) Section 1.5 Study Rationale
Clarified that subjects may start study drug on the day of the baseline visit or the following day, depending on the time of day of their visit.	Allowed IP to be started the day after the baseline visit if subjects have already missed their scheduled dosing time, to keep dosing around the same time each day.	Section 4.3 Schedule of Assessment, Table 1 Section 4.3.2.1 Baseline Visit Section 7.2.2 Selection and Timing of Dose and Administration
Removed “SAE forms and SAE Reporting instructions” and “Pregnancy Surveillance Forms” form study materials, and added “Back-up forms for CT SAE report, Exposure During Pregnancy and Pregnant Partner Release of Information”.	Aligned with Pfizer SAE reporting process and applicable study materials	Section 6.1 Study Materials
Removed “(and non-investigational product at the discretion of the investigator)”.	Clarified that management of non-investigational products is not protocol driven for early discontinuation subjects.	Section 6.5 Early Discontinuation from the Study
Updated SAE reporting destination and electronic reporting system administrative changes and clarifications.	Incorporation of non-substantial changes described in previous PACL dated 28 Apr 2023	Section 8.1.2 Collection and Reporting Serious Adverse Events
Updated text for Data Protection.	Aligned with Pfizer protocol template	Section 15 Data Protection
Added compliance aim for IP of 80%.	Defined compliance for clarity	Section 7.4 Treatment Compliance
Clarified study drug destruction.	Updated destination for study drug destruction	Section 7.5 Destruction and Return of Study Drug
Removed Clinical Protocol Approval Form.	Aligned with Pfizer protocol template	Section 16 Clinical Protocol approval form (removed)
Removed CONFIDENTIAL AND INVESTIGATOR STATEMENT.	Aligned with Pfizer protocol template	CONFIDENTIAL AND INVESTIGATOR STATEMENT (removed)
Updated the time for database lock and the type of CSR to be produced.	Updated for clarity	Section 9.4 Schedule of Analyses
Clarified that acetaminophen would be allowed during the study for acute headache.	Updated for clarity	Section 5.4 Prohibited and Restricted Concomitant Medications and Devices #5
Added reference to quality tolerance limits.	Aligned with Pfizer protocol template	Section 9.3 Statistical Methods
Removed Phase 1 study exception and the statement regarding Principal Investigator and the Sponsor’s representative signatory. Added Sponsor’s	Aligned with Pfizer protocol template	Section 10.1 Good Clinical Practice

regulatory and ethics responsibilities.		
Add the section for IRB/IEC.	Aligned with Pfizer protocol template	Section 10.3 Institutional Review Board/Independent Ethics Committee
Added Pfizer standard text for Dissemination of Clinical Study Data.	Aligned with Pfizer protocol template	Section 10.6 Dissemination of Clinical Study Data
Added AE information on lack of efficacy and medication errors.	Aligned with Pfizer protocol template	Section 8.5.4 Lack of Efficacy Section 8.5.5 Medication Errors
Added Pfizer standard safety language for environmental exposure, exposure during pregnancy, exposure during breastfeeding, occupational exposure.	Aligned with Pfizer protocol template and incorporated changes made in PACL dated 28 Apr 2023	Section 8.5 Environmental Exposure, Exposure During Pregnancy or Breastfeeding, and Occupational Exposure
Removed “read”, and clarify that subjects must sign and date an ICF for study participation.	Aligned with Pfizer standard and processes	Section 10.4 Informed Consent
Removed Names of Study Personnel.	Removed to protect personal information	Section 16.1 Appendices Names of Study Personnel (removed)
Moved prior Protocol Amendment Summary of Changes to Appendix.	Editorial	Section 16.1 Appendix 1 Protocol Amendment History
Updated List of abbreviations	Editorial	List of Abbreviations
Changed term “Non-Investigational Product”, to “Concomitant Therapy”, and updated the definition for concomitant therapy.	Aligned definition with current regulations.	Section 7.1.2 Concomitant Therapy
Corrected that non-serious AEs should be reported from signing of consent through Follow up Week 8 Visit.	Correction	Section 4.3 Schedule of Assessment, footnote #10 Section 4.3.3.2 Follow-up Week 8 Visit
Removed “provided the IRB/IEC is notified within 5 days”.	Amended to allow for immediate action to be implemented	Section 12 Amendments
Updated Publications Policy.	Updated per investigator's Clinical Research Agreement	Section 13 Publications Policy
Updated details on confidentiality and renamed section, Data Protection.	Replaced with Pfizer Data protection policy	Section 15 Data Protection
Updated the exclusion criterion number as 7g in the title.	Editorial update	Section 16.3 Appendix 3 – Categories of Migraine Prevention Medications (Reference for Exclusion Criteria 7g)
Removed the subtitle for Clinical Adverse Event Profile.	Editorial	Section 1.3.1 Clinical Adverse Event Profile

Updated document header and footer.	Updated to align with Pfizer protocol template	Header and Footer
Corrected inconsistencies and typographical errors throughout the protocol.	Corrections to provide clarity and consistency throughout the protocol.	Applicable sections of the protocol

STUDY SUMMARY (SYNOPSIS)

Protocol Title: A Phase 4, Open-label Study to Evaluate the Safety and Tolerability of Daily Dosing of Rimegepant in Episodic Migraine Prevention

Brief Title: The purpose of this study is to further evaluate the long-term safety and tolerability of daily dosing of rimegepant for the prevention of episodic migraine.

Regulatory Agency Identification Number(s):

US IND Number:	109886
EudraCT Number:	NA
ClinicalTrials.gov ID:	NCT05207865
Pediatric Investigational Plan Number:	NA
Protocol Number:	BHV3000-405 (C4951011)
Phase:	4

Rationale: This is a post marketing required study being conducted to further evaluate the long-term safety and tolerability of a more frequent daily dosing regimen of rimegepant for the prevention of episodic migraine.

Primary Objectives:

To evaluate the long-term safety and tolerability of rimegepant taken daily for episodic migraine prevention.

Primary Endpoint:

Frequencies of the following safety events and findings on treatment: AEs that occur in at least 5% of subjects by intensity; serious adverse events (SAEs); AEs leading to study drug discontinuation; and grade 3 to 4 laboratory test abnormalities.

Overall Design:

This is a multicenter, open-label study to assess the safety and tolerability of rimegepant in migraine prevention. The Screening Phase is 3-14 days in duration, followed by a Baseline Visit at which time eligibility for continued participation in the study will be assessed before study drug is dispensed. Subjects will take 1 tablet (rimegepant 75 mg ODT) each day during the Open-Label Treatment Phase. If subjects have a migraine during the Open-label Treatment Phase, then they may treat the migraine with permitted acute migraine medication as needed while continuing to take the study drug.

Study visits will occur at Screening, Baseline, Week 2, Week 4, Week 8, Week 12, Week 16, Week 20, Week 24, and End of Treatment (EOT) for early discontinuation. After the Week 24 or EOT Visit, subjects should complete the Follow-up Week 2 and Follow-up Week 8 visits for assessment of AEs and laboratory assessments.

Number of Subjects:

A sufficient number of subjects will be screened to treat up to 285 subjects with study drug to ensure that at least 170 subjects will complete 24 weeks of treatment. All subjects will be assigned to rimegepant 75 mg ODT dosed daily.

Study Population:

The study will recruit subjects 18 years of age or older with at least a one-year history of episodic migraine (with or without aura) consistent with a diagnosis according to the International Classification of Headache Disorders, 3rd edition. Per their own report, subjects must have migraine onset prior to age 50, migraine attacks that last 4-72 hours (if not treated), and have had 4-14 **migraine attacks** per 4 week period within the 12 weeks prior to the Screening Visit.

WOCBP who are unwilling or unable to use an acceptable contraceptive method or abstinence to avoid pregnancy for the entire study and for 28 days after the last dose of study drug, women who are pregnant or breastfeeding, and women with a positive pregnancy test at screening or prior to study drug administration will be excluded.

Subjects with a history of or current evidence of uncontrolled, unstable or recently diagnosed cardiovascular disease, such as ischemic heart disease, coronary artery vasospasm, and cerebral ischemia are excluded. Subjects with myocardial infarction (MI), acute coronary syndrome (ACS), percutaneous coronary intervention (PCI), cardiac surgery, stroke or transient ischemic attack (TIA) during the 6 months (24 weeks) prior to the Screening Visit will be excluded. Subjects will also be excluded who have uncontrolled hypertension (high blood pressure), uncontrolled diabetes, or a history or current evidence of any unstable medical conditions that, in the investigator's opinion, would expose them to undue risk of a significant adverse event (AE) or interfere with assessments of safety or efficacy during the course of the study

History of use of opioid- (morphine, codeine, oxycodone, hydrocodone) or barbiturate- (e.g. butalbital) containing medication for ≥ 4 days per month during the 3 months (12 weeks) prior to the Screening Visit is exclusionary.

Statistical Methods:

The frequencies of the following on-treatment safety events and findings will be presented for the safety analysis set: AEs by intensity in $\geq 5\%$ of subjects (mild, moderate, severe, total); SAEs; AEs by relationship to study drug (related, possibly related, unlikely related, not related); AEs related to study drug by intensity; AEs leading to study drug discontinuation; hepatic-related AEs by intensity; hepatic-related AEs leading to study drug discontinuation; laboratory test abnormalities by toxicity grade; LFT elevations based on fold change above ULN; and vital sign, physical measurement, and ECG abnormalities. Frequencies of safety events will be based on the number and percentage of subjects with events.

Ethical Considerations:

It is not known if it is safe to take more than 18 doses of rimegepant in 30 days. Taking into account the measures to minimize risk to subjects with episodic migraine, the potential risks associated with rimegepant are justified by the anticipated benefits that may be afforded to subjects with daily dosing regimens.

[figure not shown]

TABLE OF CONTENTS

PROTOCOL AMENDMENT SUMMARY OF CHANGES.....	2
STUDY SUMMARY (SYNOPSIS)	8
TABLE OF CONTENTS	12
LIST OF TABLES	14
LIST OF FIGURES	14
LIST OF ABBREVIATIONS	15
1 INTRODUCTION AND RATIONALE	19
1.1 Background	19
1.2 CGRP's Role in Migraine	19
1.3 Product Development Background	20
1.4 Benefit Risk Assessment	20

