1.5 Study Rationale

This post marketing required study is being conducted to further evaluate the long-term safety and tolerability of a more frequent daily dosing regimen of rimegepant for the prevention of episodic migraine for up to 24 weeks. Up to 285 subjects will dose with open-label study drug every day to ensure that at least 170 subjects will complete 24 weeks of treatment.

1.5.1 *Study Design Rationale*

This is a 24-week, multicenter, open-label evaluation of the long-term safety of rimegepant 75 mg taken daily for the prevention of episodic migraine. Subjects will be required to take 1 tablet of rimegepant 75 mg ODT **every day**.

If subjects have a migraine, they may treat the migraine with permitted acute migraine medications as needed (see [Section 5.5.2](#)) while continuing to take the study drug.

1.5.2 *Dose Selection*

The Phase 2b dose-ranging study CN170003 established that rimegepant 75 mg is the minimum effective dose for the acute treatment of migraine. The three Phase 3 studies BHV3000-301, BHV3000-302, and BHV3000-303 confirmed this efficacy using the current registrational endpoints for acute treatment of migraine. The pivotal Phase 3 Study BHV3000-305 demonstrated that rimegepant 75 mg EOD is effective and has a favorable safety profile for the prevention of migraine headache. The current study will evaluate the safety and tolerability of a more frequent daily dosing regimen in episodic migraine prevention.

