5 POPULATION

5.1 Number of Subjects

A sufficient number of subjects will be screened to treat approximately 285 subjects with study drug to ensure that at least 170 subjects will complete 24 weeks of treatment. All subjects will be assigned to rimegepant 75 mg ODT dosed daily.

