9.1 Sample Size

With a target sample size of 285 subjects in the safety analysis set and no events observed, the upper bound of a one-sided 95% confidence interval for zero observations is 0.01. Hence this sample size is large enough to rule out events that occur at rates greater than 1 case per 100 subjects.

In BHV3000-305 (C4951025) migraine-prevention study with EOD dosing, 73% of subjects in the rimegepant treatment group had ≥ 6 months (defined as ≥ 23 weeks) of double-blind or open-label rimegepant (i.e., 27% non-completion rate). In this study, it is expected that the 24-week non-completion rate will be higher due to early termination from baseline laboratory test

elevations. Assuming a 40% non-completion rate, approximately 170 subjects in the safety analysis set are expected to complete 24 weeks of treatment.

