5 SAMPLE SIZE, POWER, AND TYPE 1 ERROR

With a target sample size of 285 subjects in the safety analysis set and no events observed, the upper bound of a 1-sided 95% confidence interval (CI) for zero observations is 0.01. Hence, this sample size is large enough to rule out events that occur at rates greater than 1 case per 100 subjects.

In C4951025 (BHV3000-305) migraine-prevention study with every-other-day dosing, 73% of subjects in the rimegepant treatment group had \geq 6 months (defined as \geq 23 weeks) of double-blind or open-label rimegepant (i.e., 27% noncompletion rate). In this study, it is expected that the 24-week noncompletion rate will be higher due to early termination from baseline laboratory test elevations. Assuming a 40% noncompletion rate, approximately 170 subjects in the safety analysis set are expected to complete 24 weeks of treatment.

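### Treating 285 subjects is said to ensure at least 170 completers at 24 weeks, but the plan's own 40% non-completion rate supports only an expectation of about 171, with roughly a 57% chance of reaching 170

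*Protocol*

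**What the plan says.** Four places in the current text present 170 completers as a minimum that the number treated will secure.

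- Protocol synopsis, Number of Subjects: "treat up to 285 subjects with study drug to ensure that at least 170 subjects will complete 24 weeks of treatment".
- Protocol Section 1.5: "Up to 285 subjects will dose with open-label study drug every day to ensure that at least 170 subjects will complete 24 weeks of treatment".
- Protocol Section 5.1: "treat approximately 285 subjects with study drug to ensure that at least 170 subjects will complete 24 weeks of treatment".
- SAP Section 2.1: the same statement as Protocol 5.1, again with 285 as an approximate number.

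Two places derive the figure, and both state it as an expectation.

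- Protocol Section 9.1: "Assuming a 40% non-completion rate, approximately 170 subjects in the safety analysis set are expected to complete 24 weeks of treatment".
- SAP Section 5: "Assuming a 40% noncompletion rate, approximately 170 subjects in the safety analysis set are expected to complete 24 weeks of treatment".

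Protocol 9.1 takes the 27% non-completion seen in the earlier every-other-day prevention study as its reference and adds that "it is expected that the 24-week non-completion rate will be higher due to early termination from baseline laboratory test" elevations. The Amendment 5 summary gives the reason for moving to 285 as "Increased sample size needs in order to account for up to 40% drop out rate through 24 weeks".

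The number 285 is itself described in three ways: as an upper limit (synopsis, Section 1.5), as an approximate number (Section 5.1, SAP 2.1) and as a target sample size (Protocol 9.1, SAP 5).

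**The concern.** An expected value has been restated as a guaranteed minimum. If 170 is close to the mean of the number of completers, the study will fall short of it nearly as often as not, and no number close to the mean can be ensured. Neither document gives a probability of reaching 170. Neither gives a rule for treating more subjects if non-completion runs high, so nothing in the plan makes the stronger statement true.

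What is at stake is the credibility of the stated reason for the sample size. SAP Section 2.4 records that the target was raised to 285 treated subjects in order to secure 170 completers. A reader who takes the synopsis at its word would regard a result of, say, 163 completers as a failure of conduct. Under the plan's own assumption it would be an ordinary outcome.

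**Working it through.** **Inputs**

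- Treated subjects, n = 285 (Protocol synopsis, 1.5, 5.1, 9.1; SAP 2.1, 5).
- Assumed 24-week non-completion, 40%, so completion probability p = 0.60 (Protocol 9.1; SAP 5).
- Completer figure, 170 (same sections).
- Reference non-completion, 27% (Protocol 9.1; SAP 5).

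**Step 1: reproduce the plan's figure**

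Expected completers = n × p = 285 × 0.60 = 171. In reverse, 170 / 0.60 = 283.3, which rounds up to 284. Both agree with the stated pair of 285 treated and approximately 170 completers. There is no arithmetic error in the expectation.

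**Step 2: spread around that expectation**

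Treat subjects as independent with a common completion probability, so that X ~ Binomial(285, 0.60).

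- SD = √(285 × 0.60 × 0.40) = √68.4 = 8.3.
- The margin of the mean over 170 is 171 − 170 = 1 subject, about 0.12 SD.
- P(X ≥ 170) = 0.573 (exact).
- Central 95% range, conditional on 40%: 155 to 187.
- P(X ≥ 160) = 0.917 and P(X ≥ 157) = 0.960. These are the largest counts reached with at least 90% and at least 95% probability.

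**Step 3: how far the answer depends on the 40%**

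P(X ≥ 170) with 285 treated:

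| Non-completion | Expected completers | P(at least 170) |
|---|---|---|
| 27% | 208 | > 99.9% |
| 30% | 199.5 | > 99.9% |
| 35% | 185 | 97.4% |
| 38% | 177 | 81.1% |
| 39% | 174 | 70.2% |
| 40% | 171 | 57.3% |
| 41% | 168 | 43.7% |
| 42% | 165 | 30.8% |
| 45% | 157 | 6.4% |

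With 285 treated, non-completion would have to be no more than about 36.9% for a 90% chance of 170 completers, and no more than about 35.8% for a 95% chance.

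**Step 4: does the description of 285 matter?**

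At 40% non-completion, the smallest number treated that gives at least a 90% chance of 170 completers is 301, and for 95% it is 307. An approximate target might be stretched that far; an upper limit of 285 could not. An upper limit also allows fewer: 280 treated gives 42.9%.

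**Step 5: what depends on 170**

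- The primary estimand (SAP 3.2.1) uses the safety analysis set with a while-on-treatment strategy.
- SAP 4.1 defines enrolled, safety and follow-up safety sets, and no completer set.
- The only precision statement, ruling out event rates above 1 per 100, rests on all 285 treated subjects: 1 − 0.05^(1/285) = 0.0105, which the plan rounds to 0.01.
- For scale, the same zero-event bound is 1.75% with 170 subjects and 1.85% with 160, so a shortfall of ten completers would change little.

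**The case against.** The strongest reply is that the statistical sections already say the right thing, and that *ensure* in the other four places is a statement of purpose explaining why enrolment was inflated, not a claim about probability. That is a fair account of how such sentences come to be written, and it is why this is a wording point. It does not make the sentences accurate. They attach a numerical minimum to a specific number treated, and they say more than the derivation they rest on.

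A second reply is that 40% is a cautious allowance. The amendment rationale calls it an upper figure, and the only observed rate cited is 27%. If true non-completion is 35% or lower, 170 is very likely to be reached. This stands as a limit on the 57%, which is right only at exactly 40%. But Protocol 9.1 and SAP 5 adopt 40% as the assumption and expect a rate above 27%. Even if 40% is read as a ceiling, a claim to ensure 170 would have to hold at that ceiling, and there the chance is about 57%.

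Three stronger readings are tempting, and the documents support none of them.

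- A reader might infer that enrolment must stop at 285. Only the synopsis and Section 1.5 word it as a limit. Section 5.1, SAP 2.1 and the sample-size sections treat 285 as approximate or as a target.
- A reader might infer that 170 completers is the post-marketing requirement. The documents say that the study is required. They do not say that 170 completers is the condition.
- A reader might infer that 170 sets the precision of the safety results. No precision statement, analysis set or test uses it.

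Site-level clustering would break the independence assumption. Positive clustering widens the spread around 171 and leaves the chance near one half, so it does not rescue the claim.

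**Conclusion.** The point holds as a minor one. The claim in the synopsis, Sections 1.5 and 5.1 and SAP 2.1 goes beyond what Protocol 9.1 and SAP 5 support, which is an expectation of about 171 completers. At the assumed rate the promised minimum would be missed about 43% of the time (1 − 0.573). That figure assumes 285 treated, independent subjects and a true non-completion rate of exactly 40%. Uncertainty about the rate matters more than binomial variation, since a few percentage points either way move the chance from near certain to unlikely. For that reason the range of 155 to 187 should not be quoted without its condition.

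The consequence is limited to the completer and exposure target. No estimate, primary analysis or precision statement in the plan changes.

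**What to change.** In the protocol synopsis, Protocol Sections 1.5 and 5.1 and SAP Section 2.1, replace the promise of at least 170 completers with a statement that about 170 completers are expected if non-completion is 40%. Optionally add that, conditional on 40%, about 160 or more is reached with roughly 90% probability. Use one description of 285 throughout both documents, either a maximum or an approximate target.

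If the sponsor does intend 170 as a floor, wording alone is not enough. The plan should then state the probability wanted and either the number treated that delivers it (at 40% non-completion, 301 for 90% and 307 for 95%) or a rule for continuing enrolment until 170 complete.

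The wording change costs an edit to four passages, plus whatever is needed to align the description of 285, and does not touch procedures or analyses. Its only drawback is that the stated assurance becomes less favourable.
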